Appendix B – EQ-5D-5L

To calculate the EQ-5D-5L Index score, firstly each response will be converted to a score of 1-5:

Mobility Response	Scoring
I have no problems in walking about	1
I have slight problems in walking about	2
I have moderate problems in walking about	3
I have severe problems in walking about	4
I am unable to walk about	5
Self-Care Response	
I have no problems washing or dressing myself	1
I have slight problems washing or dressing myself	2
I have moderate problems washing or dressing myself	3
I have severe problems washing or dressing myself	4
I am unable to washing or dressing myself	5
Usual Activities	
I have no problems doing my usual activities	1
I have slight problems doing my usual activities	2
I have moderate problems doing my usual activities	3
I have severe problems doing my usual activities	4
I am unable to doing my usual activities	5
Pain / Discomfort	
I have no pain or discomfort	1
I have slight pain or discomfort	2
I have moderate pain or discomfort	3
I have severe pain or discomfort	4
I have extreme pain or discomfort	5
Anxiety / Depression	
I am not anxious or depressed	1
I am slightly anxious or depressed	2
I am moderately anxious or depressed	3
I am severely anxious or depressed	4
I am extremely anxious or depressed	5

The score from each domain will then be converted to a deduction from full health (using EQ-5D-5L value set for England) and aggregated to form the index score:

Full health (11111) =	1.000
Mobility level 1 (No problems):	0
Mobility level 2 (Slight):	0.058
Mobility level 3 (Moderate):	0.076
Mobility level 4 (Severe):	0.207
Mobility level 5 (Unable)	0.274
Self-care level 1 (No problems):	0
Self-care level 2 (Slight):	0.050
Self-care level 3 (Moderate):	0.080
Self-care level 4 (Severe):	0.164
Self-care level 5 (Unable)	0.203
Usual activities 1 (No problems):	0
Usual activities 2 (Slight):	0.050
Usual activities 3 (Moderate):	0.063
Usual activities 4 (Severe):	0.162
Usual activities 5 (Unable):	0.184
Pain/discomfort 1 (No pain):	0
Pain/discomfort 2 (Slight):	0.063
Pain/discomfort 3 (Moderate):	0.084
Pain/discomfort 4 (Severe):	0.276
Pain/discomfort 5 (Extreme):	0.335
Anxiety/depression 1 (No Anxiety)	0
Anxiety/depression 2 (Slight):	0.078
Anxiety depression 3 (Moderate):	0.104
Anxiety/depression 4 (Severe):	0.285
Anxiety/depression 5 (Extreme):	0.289

For example, the index score for a patient with health state 23245 is calculated as follows:

Full Health = 1

Mobility deduction = 0.058

Self-care deduction = 0.080

Usual Activity deduction = 0.050

Pain/discomfort deduction = 0.276

Anxiety / depression deduction = 0.289

Index Score = $1 - (0.058 + 0.080 + 0.050 + 0.276 + 0.289) = 0.247$

Appendix C – OIQoL-A

Introduction and Item Scoring

The OIQoL-A consists of 37 items; however, the first 4 items are informational only and are not included in the scoring. Therefore, up to 33 items (Q5-Q37) are included in the total score. Thirteen items are numerical rating scales (NRS) scored between 0 and 10, and the remainder are categorical items scored between 0 and 4. One item, Q26, has a “not applicable” answer option, and therefore may not be included in the total score. The scoring of individual items is summarized in the table below.

Items	Response scale	Scoring
Q 5, 6, 7 Q 9, 10, 11 Q 14 Q 15, 16, 17	11-point NRS (0-10)	0-10
Q 8, 12, 18	11 points NRS (0-100%)	0-10
Q13	5-point Likert scale: “ Not at all ” to “ Every night ”	0-4
Q 19-25 Q 34-37	5-point Likert scale: “ No difficulty ” to “ Unable to do ”	0-4
Q 26	“ Not applicable ” option included	0-4 or Missing
Q27-33	5-point Likert scale: “ Never ” to “ All the time ”	0-4

Total Score Calculation (0-100)

The total score is calculated on a 0-100 scale, where higher scores indicate a greater (negative) impact on quality of life. If all items are completed and Q26 is not marked as “not applicable,” the total score calculation is based on 33 items as follows:

$$(((Q5/10)*(1/33))+...((Q18/10)*(1/33))+((Q13/4)*(1/33))+ ((Q19/4)*(1/33))+... + ((Q37/4)*(1/33)))*100$$

If Q26 is marked as “not applicable,” or any additional items are missing as a result of incomplete data forms, the denominator weighting for each item should be the total number of completed, scored items. However, if more than 20% of the items on the instrument have missing data, the total score should not be calculated and should be considered missing.

Pain Subscale

The “worst” pain item (Q6) will be used to evaluate pain severity.

Impact on Activities of Daily Living (ADL)

Items #19-26 comprise the ADL domain, so that the subscale score is based on a total of 7 or 8 items. For example, if Q26 is not marked as “not applicable” and no items are missing:

$$[(Q19/4)*(1/8)+... ((Q26/4)*(1/8))]*100$$

If Q26 is marked as “not applicable” and no items are missing:

$$[(Q19/4)*(1/7)+... ((Q25/4)*(1/7))]*100$$

Similarly if more than 20% of the items on the instrument have missing data, the ADL subscale score should not be calculated and should be considered missing.

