10.1.4. Patient-Reported Quality of Life

The SF-12 is a generic, 12-item survey that measures 8 domains of health: physical functioning, role limitations due to physical health, bodily pain, general health perceptions, vitality, social functioning, role limitations due to emotional problems, and mental health. It yields scale scores for each of these 8 domains and 2 summary measures of physical and mental health: The Physical Component Summary and the Mental Component Summary.

The EQ-5D-5L is a standardised measure of health status comprised of a descriptive system of 5 health-related quality of life states (i.e., mobility, self-care, usual activities, pain/discomfort, and anxiety/depression) and a Visual Analogue Scale (VAS) of overall health. Each dimension is rated on a 5-point response scale indicating severity of problems, where 1 is "no problems" and 5 is "extreme problems". The 5 questions are scored and together contribute to the EQ-5D index (utility) score between 0 and 1 (1 being perfect health), which will be calculated using the developers' algorithm based on country-specific reference score sets. The EQ-5D VAS is a measure of overall self-rated health status, used and analysed separately from the index score. The VAS ranges from 0 to 100, with higher scores indicative of better overall health.

The OIQoL-A is a PRO instrument for use in adults with OI Type I, III, or IV. The OIQoL-A currently measures 5 areas of quality of life related to OI (Physical Function, Pain, Hearing Loss, taking care/Concerns, Social and Family Life and Activities); data collected from the phase 2b trial will be used to validate the instrument prior to its use within the phase 3 study.

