 - 9 mediated degradation of Type V collagen [C5M]
18. Change in total scores from baseline to Month 6 and 12 on Short Form 12 Health Survey (SF-12), EuroQol 5-dimension 5-level descriptive system (EQ-5D-5L) and Osteogenesis Imperfecta specific Quality of Life Questionnaire for Adults (OIQoLA)
19. Change in OIQoL-A pain and activity subscale scores from baseline to Month 6 and 12
20. Serum concentrations of setrusumab
21. Serum concentrations of anti-setrusumab antibodies
22. Serum concentrations of setrusumab neutralising antibodies
23. Safety and Tolerability endpoints including:
 - Treatment-emergent adverse events (TEAEs)/Treatment-emergent serious adverse events (TESAEs)
 - Infusion site reactions
 - Vital signs
 - Physical examinations
 - ECG
 - Clinical laboratory tests

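### SAP Appendix C ties the missing-item limit for the OIQoL-A activity (ADL) subscale to the whole instrument, not the subscale's own 7 or 8 items, and gives no denominator for a partly answered subscale

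*SAP*

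**What the plan says.** SAP Section 4.2 lists as a secondary endpoint: "Change in OIQoL-A pain and activity subscale scores from baseline to Month 6 and 12". Section 8.5.3.8.3 analyses the activity score by ANCOVA on change from baseline at each treatment-period visit.

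Scoring is in SAP Appendix C:

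- Length of the questionnaire: "The OIQoL-A consists of 37 items; however, the first 4 items are informational only and are not included in the scoring".
- Base of the total score: "Therefore, up to 33 items (Q5-Q37) are included in the total score".
- ADL subscale: "Items #19-26 comprise the ADL domain, so that the subscale score is based on a total of 7 or 8 items". It has 7 items when Q26 is marked not applicable.
- Missing-data limit for the total score: "if more than 20% of the items on the instrument have missing data, the total score should not be calculated and should be considered missing".
- Missing-data limit for the ADL subscale: "Similarly if more than 20% of the items on the instrument have missing data, the ADL subscale score should not be calculated".
- Denominator when items are missing, given under the total score only: "the denominator weighting for each item should be the total number of completed, scored items".

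The two ADL formulas cover only the cases with no missing items, one with Q26 applicable and one without. SAP Section 7.2.2.2 says that missing items follow each questionnaire author's recommendation and refers to Section 7.1.3. For the OIQoL-A, Section 7.1.3.6 refers on to Appendix C, so Appendix C holds the only rule.

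**The concern.** A missing-item limit should ensure that a score rests on enough of its own items. A limit on the whole questionnaire does not do that for an 8-item subscale. It can let a mostly blank subscale through, and it can reject a complete one because of blanks that have nothing to do with activity.

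Appendix C is also uneven on this. Pain severity is taken from Q6 alone with no whole-instrument condition. A patient with many blanks elsewhere keeps the pain score but loses a fully answered activity score.

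What is at stake is one patient-reported secondary endpoint. SAP Section 7.2.1 presents summaries on observed cases without imputation, and no imputation is given for a voided score. With 25 participants planned per arm, each voided score costs 1/25 = 4% of an arm at that visit. A voided baseline score removes that patient's change from baseline at every visit. Protocol Section 10.1.4 adds a further use: "data collected from the phase 2b trial will be used to validate the instrument prior to its use within the phase 3 study". An unclear subscale rule would carry into that work.

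**Working it through.** **Item count (the plan's own figure).** From the item table in SAP Appendix C:

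- Numerical rating items: Q5–7 (3), Q9–11 (3), Q14 (1), Q15–17 (3), and Q8, Q12, Q18 (3), giving 13.
- Categorical items: Q13 (1), Q19–25 (7), Q26 (1), Q27–33 (7), Q34–37 (4), giving 20.
- 13 + 20 = 33, covering Q5 to Q37 without gap or overlap. The stated 33 is reproduced.

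**The limit.** For a base of N items, the largest permitted number of blanks is the largest whole m with m/N ≤ 0.20. The score is void at m + 1. If all m blanks fall in the ADL subscale, the number of ADL items answered is its size minus m. A complete ADL subscale can be voided if there are at least m + 1 items outside it.

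On the 33 scored items:

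- 0.20 × 33 = 6.6, so m = 6. Six blanks are 6/33 = 18.2% (within the limit) and seven are 7/33 = 21.2% (void).
- All six in the ADL subscale: 8 − 6 = 2 answered, so 6/8 = 75% of the subscale is blank and the limit is not crossed.
- All eight ADL items answered: 33 − 8 = 25 items lie elsewhere, and seven blanks among them void the score.

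**Other bases.** Appendix C does not say which base applies. Its item table codes a not-applicable Q26 as 0–4 or missing, and the text does not say whether that answer counts towards the 20%.

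| Base | 20% of base | Most blanks allowed | Void at | Fewest ADL items answered within the limit | Can a complete ADL subscale be voided? |
|---|---|---|---|---|---|
| 33 scored items | 6.6 | 6 (18.2%) | 7 (21.2%) | 2 of 8 | Yes, 25 other items |
| 32 (Q26 not applicable, left out) | 6.4 | 6 (18.8%) | 7 (21.9%) | 1 of 7 | Yes, 25 other items |
| 33, not-applicable Q26 counted as a blank | 6.6 | 6, so 5 besides Q26 | 7, so 6 besides Q26 | 2 of 7 | Yes, 25 other items |
| All 37 items | 7.4 | 7 (18.9%) | 8 (21.6%) | 1 of 8 | Yes, 29 other items |
| 36 (37 less a not-applicable Q26) | 7.2 | 7 (19.4%) | 8 (22.2%) | 0 of 7 (nothing to score) | Yes, 29 other items |

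The counts move with the base. The last column does not.

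**The same 20% on the ADL items themselves.** 0.20 × 8 = 1.6 and 0.20 × 7 = 1.4, so one blank is allowed in either case: 1/8 = 12.5% or 1/7 = 14.3%. Two are void: 2/8 = 25% or 2/7 = 28.6%. A score then needs at least 7 of 8 or 6 of 7 items, and blanks elsewhere cannot void a complete subscale.

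**What two items can do to a score.** This assumes the completed-items denominator is carried over from the total score. Items run 0–4 and the subscale 0–100.

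- Six items at 4 and two at 0: complete score 6/8 × 100 = 75. If only the two zeros are answered, the score is 0.
- Two items at 4 and six at 0: complete score 2/8 × 100 = 25. If only the two fours are answered, the score is 100.

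These are extremes that show the possible distortion, not forecasts.

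**The case against.** **The plan does not actually say to score from 2 items.** A reader might infer that Appendix C instructs a score from 2 of 8 items. It does not. It describes the score as resting on 7 or 8 items, both ADL formulas assume none is missing, and the completed-items denominator is written only under the total score. This stands. What the text supports is narrower: the limit does not prevent such a score, and nothing says how a partly answered subscale is to be scored. Reading the 7-or-8 phrase as barring any fewer does not rescue the rule, because the 20% sentence would then have little work to do for this subscale.

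**The figures depend on the base.** This also stands. On all 37 items, seven blanks are 18.9% and void nothing; eight are needed. So 2 of 8 and seven blanks belong to the 33-item base only.

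**Instrument may be a slip for subscale.** That is possible, since the sentence closes the ADL paragraph and may have been carried over from the total score. But the same phrase governs the total score, and Protocol Section 10.1.4 uses the word for the whole OIQoL-A. A programmer would reasonably apply one whole-questionnaire check to both scores. If it is a slip, the same edit cures it.

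**The rule may be the developer's own.** SAP Section 7.2.2.2 relies on the author's recommendation, which the documents do not contain. A whole-form completeness rule is coarse but not indefensible. This is a reason to check the source before editing. It does not remove the consequences of the rule as written.

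**Conclusion.** The point holds in this form: the ADL subscale's only missing-data limit is set on the whole questionnaire, its base is not stated, and no denominator is given when ADL items are missing. Under every whole-instrument base, blanks outside the subscale can void a fully answered one. A mostly blank subscale can also stay within the limit: 2 of 8 answered on the 33-item base, 1 of 8 on 37, and 1 of 7 on 32. That such a score would in fact be produced is an assumption, resting on the total-score denominator carrying over.

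The practical weight is small. The documents give no item-level missingness, so the frequency is unknown. The harm needs several blanks concentrated inside, or entirely outside, one block of items. It touches one subscale of a secondary endpoint and leaves the primary analysis alone. It is a minor point, worth correcting because the correction is nearly free.

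**What to change.** First check Appendix C against the developer's scoring guidance on which SAP Section 7.2.2.2 relies. If the whole-instrument limit is the developer's rule, say so and confirm that it was meant for this subscale.

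Unless that guidance directs otherwise, amend the ADL paragraph of Appendix C to state that:

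- the 20% limit applies to Q19–Q26, or to Q19–Q25 when Q26 is not applicable, so at most one applicable item may be missing;
- the score is the mean over the completed ADL items, rescaled to 0–100;
- a not-applicable Q26 does not count as missing.

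The cost is a sentence or two in the SAP and a matching change to the scoring program, best made before unblinding. No data collection changes.
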